5.1.6. Visit 3 / Week-8 (28 days +/- 4 days after last visit)

Visit 3 will be performed at OHSU or optionally by telemedicine and REDCap survey.

- Study personnel will gather the following information from the subjects and record the results in REDCap:
 - Change in medications since the last visit
 - Change in drug allergies since the last visit
 - Change in personal or family medical history, including adverse events, since the last visit
 - Weight (performed by the subject for videoconferencing visits)
 - Blood pressure (performed by the subject for videoconferencing visits)
 - Pulse (performed by the subject for videoconferencing visits)
- Subjects will enter the following information about their disease and medical history via OHSU REDCap survey:
 - DLQI
 - PSSD PSSD
 - iPRPASI

- The subject will be clinically examined by an investigator (clinician or research nurse, either in-person or via telemedicine) who will assess the following:
 - Full body skin exam with documentation of PASI, PGA, and PPPGA

5.1.7. Visit 4 / Week-12 (28 days +/- 4 days after last visit)

Visit 4 will be performed at OHSU or optionally by telemedicine and REDCap survey for subjects who live >30 miles from OHSU.

- Study personnel will gather the following information from the subjects and record the results in REDCap:
 - Change in medications since the last visit
 - Change in drug allergies since the last visit
 - Change in personal or family medical history, including adverse events, since the last visit
 - Weight (performed by the subject for videoconferencing visits)
 - Blood pressure (performed by the subject for videoconferencing visits)
 - Pulse (performed by the subject for videoconferencing visits)
- Subjects will enter the following information about their disease and medical history via OHSU REDCap survey:
 - DLQI
 - PSSD
 - iPRPASI
- The subject will be clinically examined by an investigator (clinician or research nurse, either in-person or via telemedicine) who will assess the following:
 - Full body skin exam with documentation of PASI, PGA, and PPPGA
- The third dose of 100 mg of subcutaneous guselkumab will be administered by the subject with observation and teaching from study personnel.
- Blood will be drawn for CBC, CMP (for telemedicine visits this will be done at a local lab of the subject's choice within +/- 2 days of the visit)

5.1.8. Visit 5 / Week-20 (56 days +/- 7 days after last visit)

Visit 5 will be performed at OHSU or optionally by telemedicine and REDCap survey for subjects who live >30 miles from OHSU.

- Study personnel will gather the following information from the subjects and record the results in REDCap:
 - Change in medications since the last visit
 - Change in drug allergies since the last visit
 - Change in personal or family medical history, including adverse events, since the last visit
 - Weight (performed by the subject for videoconferencing visits)
 - Blood pressure (performed by the subject for videoconferencing visits)
 - Pulse (performed by the subject for videoconferencing visits)
- Subjects will enter the following information about their disease and medical history via OHSU REDCap survey:
 - DLQI
 - PSSD
 - iPRPASI
- The subject will be clinically examined by an investigator (clinician or research nurse, either in-person or via telemedicine) who will assess the following:
 - Full body skin exam with documentation of PASI, PGA, and PPPGA
- The fourth dose of 100 mg of subcutaneous guselkumab will be administered by the subject with observation and teaching from study personnel.

5.1.9. Visit 6 / Week-24 (primary endpoint; 28 days +/- 4 days after last injection)

Visit 6 will be performed at OHSU for all subjects.

- Study personnel will gather the following information from the subjects and record the results in REDCap:
 - Change in medications since the last visit
 - Change in drug allergies since the last visit
 - · Change in personal or family medical history, including adverse events, since the last visit
 - Weight
 - Blood pressure
 - Pulse
- Subjects will enter the following information about their disease and medical history via OHSU REDCap survey:
 - DLQI
 - PSSD
 - iPRPASI
- The subject will be clinically examined by an investigator (clinician or research nurse) who will assess the following:
 - Full body skin exam with documentation of PASI, PGA, PPPGA, and NAPSI
 - Examination of the oral mucosa
 - Heart and lung auscultation
 - Palpation of the cervical, axillary, and inguinal lymph nodes
 - Presence of peripheral edema
- Photographs will be taken against a dark backdrop with standardized poses according to published recommendations (*31*), with the addition of focused photographs of the palms and nails.
- Blood will be drawn for monitoring the CBC, CMP, and measuring levels of inflammation
- Subjects will undergo a punch biopsy (consisting of three adjacent 3 mm punch biopsies, a total surface area equivalent to the size of a 5 mm punch biopsy) in the same body region as the first documented biopsy (back, chest, arm, or leg), preferably in an area affected by PRP at the first study visit and possibly cleared or improved at the endpoint visit.

5.1.10. Visit 7 / Week-36 (56 days +/- 7 days after last visit)

Visit 7 will be performed at OHSU or optionally by telemedicine and REDCap survey for subjects who live >30 miles from OHSU.

- Study personnel will gather the following information from the subjects and record the results in REDCap:
 - Change in medications since the last visit
 - Change in drug allergies since the last visit
 - Change in personal or family medical history, including adverse events, since the last visit
 - Weight (performed by the subject for videoconferencing visits)
 - Blood pressure (performed by the subject for videoconferencing visits)
 - Pulse (performed by the subject for videoconferencing visits)
- Subjects will enter the following information about their disease and medical history via OHSU REDCap survey:
 - DLQI
 - PSSD
 - iPRPASI
- The subject will be clinically examined by an investigator (clinician or research nurse, either in-person or via telemedicine) who will assess the following:
 - Full body skin exam with documentation of PASI, PGA, and PPPGA

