therapy that would pose an unacceptable risk to the subject if participating in this study.
 Have or intend to have a live vaccine within 3 months prior to baseline or 12 months prior to baseline in the case of the BCG vaccine, or any live vaccine during the course of study or within 3 months after the last administration of study drug.
 Had any major surgery within 8 weeks prior to baseline or will require major surgery during the study, that in the opinion of the investigator would pose an unacceptable risk to the subject.
 Presence of significant uncontrolled cerebrovascular, respiratory, hepatic, renal, gastrointestinal, endocrine, hematologic, neurologic, or neuropsychiatric disorders, or abnormal laboratory screening values that, in the opinion of the investigator, pose an unacceptable risk to the subject if participating in the study or of interfering with the interpretation of the data.
 Have clinical laboratory test results at screening that are outside the normal reference range of the population and are considered clinically significant, or have any of the following specific abnormalities: Neutrophil count <1500 cells/µL, white blood cell count <3500 cells/µL, platelet count <100,000 cells/µL, AST or ALT or alkaline phosphatase > 2 times the upper limit of normal, hemoglobin <10 g/dL, serum creatinine >1.5 mg/dL. A single retest of laboratory values is permitted if one or more values is out of range.
 Women who are lactating or breastfeeding.
 Have any other condition that precludes the subject from
following and completing the protocol, in the opinion of the investigator.
 Are investigator site personnel directly affiliated with this study and/or their immediate families (spouse, parent, child, or

	 sibling). Are currently enrolled in, or discontinued from a clinical trial involving an investigational product or non-approved use of a drug or device within the last 4 weeks or a period of at least 5 half-lives of the last administration of the drug, whichever is longer, or concurrently enrolled in any other type of medical research judged not to be scientifically or medically compatible with this study.
Description of Interventions	Subjects with PRP will be treated with guselkumab for 20 weeks using the FDA-approved dosing schedule for psoriasis (100 mg subcutaneous injection at weeks 0, 4, 12, and 20).
Duration of Study	The duration of the study will be 36 weeks

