3.2.3. Secondary Endpoints Assessed by Subject

 Proportion of subjects achieving a 4-point improvement in quality of life measured by the Dermatology Life Quality Index (DLQI) at week-24, proportion of patients achieving a DLQI of 0 or 1 at week-24, and mean improvement in DLQI score at week-24. The DLQI (26) is a validated tool for inflammatory skin conditions. It is a 10-question survey, scored 0 – 30 points. For inflammatory skin conditions, a 4-point change in DLQI score is considered clinically important (27).

- Mean percentage in improvement in Psoriasis Symptoms and Signs Diary (PSSD) at week-24, and proportion of patients achieving a PSSD of zero at week-24. The PSSD is an 11-question 0 – 10-point numeric rating scale (NRS) patient-reported outcome measure assessing itch, dryness, cracking, skin tightness, scaling, shedding or flaking, bleeding, burning, stinging, and pain over the last 24 hours and 7 days respectively (28).
- Mean change from baseline individual PRP Area and Severity Index (iPRPASI) at week-24 after treatment with guselkumab, and correlation of subject-assessed iPRPASI scores with investigator-assessed PASI scores. The IPRPASI is a novel subject self-assessment score of disease involvement and severity, based on a previously published similar tool validated for psoriasis (29).
- Sustained remission at week-36, 16 weeks after the last guselkumab dose, as measured by the mean change in PASI from week-24 to week-36. Sporadic PRP is often a self-limited disease, resolving spontaneously after an average of 3-6 years. Other immunomodulatory medications have induced sustained remission of PRP (22), so there is a potential that treatment may "reset" the immune response and lead to long-term improvement in the disease, especially in subjects without genetic mutations. Subjects will be treated with guselkumab as per the FDA-approved psoriasis treatment guidelines, and therapy will be stopped after the 20-week dose. Subjects will be monitored at 24 weeks (primary study endpoint) and then at 36 weeks to assess for sustained remission versus relapse.

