7.2.3. Exploratory Endpoint Analyses

- Sustained remission at week-36, measured by the mean change in PASI score from week-24 to week-36, will be analyzed for statistical significance using a paired, two-tailed Student's t-test.
- Treatment response, as measured by PASI 50, will be stratified by CARD14 germline mutations. The proportion of subjects with a PASI 50 response with and without CARD14 mutations will be reported and compared for statistical significance using an unpaired, two-tailed Student's t-test.
- Epithelial expression of CARD14 will be assessed qualitatively by a trained dermatopathologist who is blinded to the biopsy collection time (before or after therapy).
- The gene expression level from the tissue biopsy, before, 4 weeks, and 24 weeks after treatment, will be analyzed for statistical significance using a pared, two-tailed Student's t-test and also compared with normal and psoriatic skin using a two-tailed, two-sample Student's t-test with unequal variance adjusted for multiple comparisons.
- The cytokine level from serum before, 4 weeks, and 24 weeks after treatment, will be analyzed for statistical significance using a pared, two-tailed Student's t-test and also compared with normal and psoriatic serum using a two-tailed, two-sample Student's t-test with unequal variance adjusted for multiple comparisons.

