8. SAFETY

8.1. Specification of Safety Parameters

As the sponsor of the Study, OHSU and the PI shall be solely responsible for complying, within the required timelines, any safety reporting obligation to competent Health Authorities, IRB and any participating (co or sub) investigators, as defined in applicable laws and regulations. For the purposes of this protocol, safety data includes adverse events, product quality complaints (PQCs), and special situations including pregnancies. Safety assessments will be based on medical review of adverse events and the results of safety evaluations at specified time points as described in Section 5.1 Study Visit Procedures. Any clinically significant adverse events persisting at the end of treatment visit will be followed by the Investigator until resolution/stabilization or death, whichever comes first.

OHSU and the PI will provide safety information to Janssen Scientific Affairs on adverse events, special situations including pregnancies and product quality complaints as defined within this protocol.

This Study has been designated as an interventional study. As such, all adverse events for Janssen Study drugs regardless of causality and special situations excluding those from subjects not exposed to a Janssen Study drug and product quality complaints with or without an adverse event as described in this Protocol will be reported from the time a subject has signed and dated an Informed Consent Form (ICF) until completion of the subject's last study-related procedure (which may include contact for follow-up safety). Serious adverse events will be reported up to week-36 (16 weeks after the last dose of study drug).

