8.3. Adverse Event Assessment and Follow-Up

The occurrence of an UP, AE or SAE may come to the attention of study personnel during study visits and interviews of a study participant presenting for medical care, or upon review by the PI. All AEs including local and systemic reactions not meeting the criteria for SAEs will be captured on the appropriate eCRF. Information to be collected includes event description, time of onset, clinician's assessment of severity, seriousness, expectedness, relationship to study product (assessed only by those with the training and authority to make a diagnosis), and date of resolution/stabilization of the event. All AEs occurring while on study must be documented appropriately regardless of relationship. All AEs will be followed to adequate resolution.

Any medical condition that is present at the time that the participant is screened will be considered as baseline and not reported as an AE. However, if the study participant's condition deteriorates at any time during the study, it will be recorded as an AE.

Changes in the severity of an AE will be documented to allow an assessment of the duration of the event at each level of severity to be performed. AEs characterized as intermittent require documentation of onset and duration of each episode.

At each study visit, the Investigator will inquire about the occurrence of AE/SAEs since the last visit. Events will be followed for outcome information until resolution or stabilization.

The Investigator will record all reportable events with start dates occurring any time after informed consent is obtained until the week-36 follow-up study visit. Any SAE that occurs after treatment with alternative therapy will be reported only if the Investigator or current treating physician has assessed the SAE as related to the study treatment.

All serious adverse events that have not resolved by the end of the study, or that have not resolved upon discontinuation of the subject's participation in the study, will be followed until any of the following occurs:

- The event resolves
- The event stabilizes
- The event returns to baseline, if a baseline value/status is available
- The event can be attributed to agents other than the study drug or to factors unrelated to study conduct

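### The Visit 7 interval of 56 ± 7 days puts the visit at about week 32, 73–95 days after the last dose, not at week 36 and 112 days as stated elsewhere

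*Combined protocol and SAP*

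**What the plan says.** The heading of section 5.1.10 gives a week label and an interval together: "Visit 7 / Week-36 (56 days +/- 7 days after last visit". The visit before it is headed, in section 5.1.9, "Visit 6 / Week-24 (primary endpoint; 28 days +/- 4 days after last injection". The last dose is the fourth, given at Visit 5 (week 20; sections 5.1.8 and 6.2).

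Two sections tie week 36 to the last dose. Section 3.2.3 has "Sustained remission at week-36, 16 weeks after the last guselkumab dose", and section 8.1 has "Serious adverse events will be reported up to week-36 (16 weeks after the last dose of study drug". Section 7.2.3 analyses the endpoint as "Sustained remission at week-36, measured by the mean change in PASI score from week-24 to week-36", by a paired t-test. Section 8.3 records events from "any time after informed consent is obtained until the week-36 follow-up study visit". The synopsis states "The duration of the study will be 36 weeks", and its visit list, section 3.1, section 5.2 and Table 1 also use week 36.

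The table of contents repeats the 5.1.10 heading with the same 56-day interval. Nothing in the protocol reconciles the interval with the week-36 label.

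**The concern.** The label and the interval in the same heading cannot both hold: 56 days after week 24 is week 32. Three things depend on which one is followed.

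- **Endpoint.** Sustained remission is measured by the PASI change between Visits 6 and 7. That change covers 8 weeks under the interval and 12 under the label. If practice differs between subjects, one paired t-test on at most about 15 people would mix 8-week and 12-week changes.
- **Safety period.** Section 8.3 ends event recording at the final visit, while section 8.1 runs SAE reporting to 16 weeks after the last dose. A final visit at week 32 leaves about 4 weeks between the two.
- **Visit window.** If staff schedule by the label after an on-time Visit 6, the visit falls outside the window printed in its own heading.

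An earlier assessment would flatter durability only if PASI worsens with time off drug. The documents do not establish that, so no direction of bias is claimed.

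**Working it through.** **Inputs.** Visit intervals come from the headings of sections 5.1.5 to 5.1.10. The last dose is at week 20 (sections 5.1.8 and 6.2). The stated distance from last dose to week 36 is 16 weeks (sections 3.2.3 and 8.1).

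**1. The stated figure, from the week labels.** Last dose to week 36: (36 − 20) × 7 = 112 days = 16 weeks. Week 24 to week 36: (36 − 24) × 7 = 84 days. The week labels and the 16-week statements therefore agree with each other.

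**2. The intervals, added up from baseline.**

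| Visit | Interval (days) | Nominal day | Nominal week | Labelled week |
|---|---|---|---|---|
| 2 | 28 ± 4 | 28 | 4 | 4 |
| 3 | 28 ± 4 | 56 | 8 | 8 |
| 4 | 28 ± 4 | 84 | 12 | 12 |
| 5 | 56 ± 7 | 140 | 20 | 20 |
| 6 | 28 ± 4 | 168 | 24 | 24 |
| 7 | 56 ± 7 | 224 | 32 | 36 |

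Only Visit 7 disagrees with its label: 252 − 224 = 28 days.

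**3. Visit 7 counted from the last dose.**

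- Visit 6: 28 ± 4 = 24 to 32 days after the last injection.
- Visit 7: 56 ± 7 = 49 to 63 days after Visit 6.
- Sum: 24 + 49 = 73 to 32 + 63 = 95 days; nominal 28 + 56 = 84 days.
- Shortfall against 112: 112 − 95 = 17 to 112 − 73 = 39 days; nominal 28 days.

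**4. Whether another reading closes the gap.** The table of contents counts Visit 6 from the last visit and the body counts it from the last injection. The result is the same, because the last injection is given at Visit 5. Adding all windows from baseline, Visit 7 can fall between days 194 and 254. Reaching day 252 needs at least 28 of the 30 available days of delay (4 + 4 + 4 + 7 + 4 + 7 = 30), and even then Visit 7 is at most 95 days after the last dose. The 16-week statement cannot be met within the windows.

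**5. If week 36 is followed instead.** After an on-time Visit 6, the visit is 84 − 63 = 21 days past the upper window limit. If exactly 112 days after the last dose is kept, Visit 7 falls 112 − 32 = 80 to 112 − 24 = 88 days after an in-window Visit 6, which is 17 to 25 days past the 63-day limit.

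**The case against.** The best defence is that this is a copying slip that would mislead nobody. Week 36 appears throughout the protocol, including in the Visit 7 heading itself. Against it stands one parenthesis, which the table of contents merely repeats. The same interval is correct two visits earlier, in "Visit 5 / Week-20 (56 days +/- 7 days after last visit", so a carry-over is plausible. At a single centre with 15 subjects, staff may well schedule from Table 1. This has force on likelihood, but the documents do not show which timing was intended, and the visit heading is where staff would look for the window.

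Other points limit the consequences, and they stand:

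- The protocol sets no rule on deviations from visit windows. A week-36 visit can be called outside its stated window, and no more than that.
- The SAE horizon in section 8.1 is stated independently of when Visit 7 occurs, and that section allows for follow-up safety contact. The problem is a conflict between sections 8.1 and 8.3 if Visit 7 is early; it is not a shown loss of SAE reports.
- The affected analysis is secondary in section 3.2.3 and exploratory in section 7.2.3, in an uncontrolled pilot.
- The 73–95 day range does not apply to subjects who stop drug early, whose week-24 visit section 8.7.1 brings forward.

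None of this removes the contradiction.

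**Conclusion.** The concern holds. As written, Visit 7 is nominally at week 32 and 84 days (73–95) after the last dose, against the stated week 36 and 112 days. The interval from Visit 6 is 49–63 days, against 84. These figures assume that the week-20 dose is given at Visit 5 and that Visit 6 is held within its window.

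The consequences for the sustained-remission interval and for event recording arise if the 56-day interval is followed for some or all subjects. This should be fixed: the error is certain and cheap to correct, but it touches neither the primary endpoint nor the power calculation.

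**What to change.** Decide which timing is intended and make every passage agree.

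- **If week 36, 16 weeks after the last dose, is kept:** change the interval in the 5.1.10 heading from 56 to 84 days after Visit 6, keeping ± 7 days. Visit 7 then falls 24 + 77 = 101 to 32 + 91 = 123 days after the last dose, nominally 112. An optional alternative is to count 112 ± 7 days from the last injection, which gives 105–119 days. That holds time off drug more tightly but lets the Visit 6 to Visit 7 interval range from 105 − 32 = 73 to 119 − 24 = 95 days, against 77–91 with the first option. Replacing 56 with 84 is sufficient.
- **If 56 days after Visit 6 is intended:** relabel as week 32, 12 weeks after the last dose, in the synopsis (visit list, duration, outcomes), sections 3.1, 3.2.3, 5.1.10, 5.2, 7.2.3, 8.1 and 8.3, and Table 1.

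In either case, bring the table of contents into line. Keeping week 36 costs one number in the heading, the table of contents and the visit scheduler, with no extra visit or subject. The week-32 route needs a wider edit and shortens the stated follow-up by 4 weeks.

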5.2. Early Withdrawal / Unscheduled Visits

If the subject wishes to withdraw from the trial before week-24, they will be asked to attend for a final trial (early termination) visit. At this visit, if the subject is willing, the same procedures as for the primary outcome / week-24 visit will be carried out. If the subject withdraws after the week-24 visit, the final week-36 visit will be carried out early instead.

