6.2. Dosing and Administration

Guselkumab treatment will be administered at the FDA-approved dosing schedule for psoriasis as follows:

• 100 mg SC injection at week-0, week-4, week-12, and week-20

The 1 mL single-dose pre-filled syringe will be injected at room temperature into the subcutaneous tissue of the upper arms, thighs, or abdomen, avoiding areas affected by PRP when possible. Each injection will be administered in an anatomic location different from the previous injection, and the location will be recorded. Injections will be performed by qualified study personnel or by the subject after proper training in SC injection technique. Injections performed at home by the subject will be recorded by the subject in an injection diary and returned to the investigators.

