8.7.2 Subject Withdrawal from the Study

A subject will be withdrawn from the study for any of the following reasons:

- Lost to follow-up
- Withdrawal of consent
- Death
- Investigator decision (e.g., participating in any other clinical study with an investigational agent)

When a subject withdraws before completing the study, the reason for withdrawal will be documented in the eCRF. Additional subjects may be enrolled to ensure the protocol-specified number of participants complete the study. If a subject withdraws after the first dose of study drug and before week-24, the week-24 study visit will be performed early if the subject is willing and able to participate. If a subject withdrawal is withdrawal of consent then no additional assessments will be performed.

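### A week-36 visit brought forward for subjects who leave after week 24 can enter the sustained-remission analysis well short of the 16 weeks off drug that define the endpoint, and the plan has no rule for it

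*Combined protocol and SAP*

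**What the plan says.** Section 3.2.3 defines the endpoint: "Sustained remission at week-36, 16 weeks after the last guselkumab dose, as measured by the mean change in PASI from week-24 to week-36". It also gives the purpose: "Subjects will be monitored at 24 weeks (primary study endpoint) and then at 36 weeks to assess for sustained remission versus relapse". The 16 weeks agrees with the dosing in Section 6.2: "100 mg SC injection at week-0, week-4, week-12, and week-20".

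Section 5.2 covers exits after week 24: "If the subject withdraws after the week-24 visit, the final week-36 visit will be carried out early instead". For exits before week 24 the same paragraph uses the term early termination. For later exits it keeps the week-36 name. Visit 7 includes a PASI (Section 5.1.10).

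Section 7.2.3 gives the analysis: "Sustained remission at week-36, measured by the mean change in PASI score from week-24 to week-36, will be analyzed for statistical significance", by a paired two-tailed t-test. Section 7 has no window for week 36, no minimum time since the last dose, no rule for a visit held early and no missing-data rule.

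Two clauses in Section 8.7.2 limit or complicate the picture. One excludes some leavers from any early visit: "If a subject withdrawal is withdrawal of consent then no additional assessments will be performed". The other permits replacement: "Additional subjects may be enrolled to ensure the protocol-specified number of participants complete the study". Its effect on the week-36 analysis is not stated.

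The visit's own timing is also inconsistent: "5.1.10. Visit 7 / Week-36 (56 days +/- 7 days after last visit". The endpoint is listed as secondary in Section 3.2.3 and as exploratory in Section 7.2.3.

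**The concern.** This is the trial's only analysis of whether response lasts after treatment stops. A conduct rule (hold the visit early) meets an endpoint tied to a fixed off-drug interval, and nothing in the analysis section separates the two. The record made at an early exit carries the week-36 label, so a programmer following the text would probably enter it as week 36.

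The consequence is asymmetric. A small or non-significant rise in PASI is the result that would be read as sustained remission. If subjects leave while the disease is returning, a score taken part-way through that return pulls the mean rise toward zero. With about 15 subjects, two or three such records move the mean visibly.

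**Working it through.** **1. Timing.** The last dose is at week 20 (Section 6.2).
- Week 36: 36 − 20 = 16 weeks after the dose, which agrees with Section 3.2.3.
- Exit at week 25: 25 − 20 = 5 weeks. Exit at week 28: 8 weeks. The interval between the last two doses is itself 20 − 12 = 8 weeks.
- Visit 7 as scheduled in Section 5.1.10: 24 + 56/7 = week 32, range 31 to 33, so 11 to 13 weeks after the dose. Week 36 would be 12 × 7 = 84 days after week 24.

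**2. The plan's own figure.** The only design calculation is power for the primary endpoint. With n = 10, change 8, SD 8 and two-sided 0.05, the exact noncentral-t calculation (9 df, noncentrality (8/8)√10 = 3.16) gives 0.8031, as printed in Section 7.1. It is not in dispute and says nothing about week 36. Everything below is illustration on assumed inputs.

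**3. Same steady worsening in everyone.** Suppose *k* of 15 leave at week *w* and are scored as week 36. The share of the true week-24 to week-36 mean change that is retained is 1 − (k/15)·(1 − (w − 24)/12).

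| Exit week | k = 1 | k = 3 | k = 5 |
|---|---|---|---|
| 26 | 0.944 | 0.833 | 0.722 |
| 28 | 0.956 | 0.867 | 0.778 |
| 32 | 0.978 | 0.933 | 0.889 |

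As a check, k = 3 and w = 28 gives 1 − (3/15)(8/12) = 0.867. The formula is symmetric. If PASI is still falling after week 24, the same shares mean that improvement is understated, and the bias runs against the drug.

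**4. Leavers are relapsers.** Assume 9 of 15 would rise by 10 points by week 36 and 6 would not change, so the true mean is 90/15 = 6.0. Let *k* relapsers leave when a fraction *f* of the rise is present, at *t* = 12*f* weeks after week 24.
- Early score used as week 36: (10(9 − k) + 10fk)/15
- Leavers excluded: 10(9 − k)/(15 − k)
- Early score kept at its actual time (straight line through the week-24 value, read off at 12 weeks): 12·[12·10(9 − k) + k·t·10f] / [144(15 − k) + k·t²]

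| k, f | As week 36 | Excluded | Actual time |
|---|---|---|---|
| 3, 0.50 | 5.0 | 5.0 | 5.3 |
| 3, 0.15 | 4.3 | 5.0 | 5.0 |
| 6, 0.50 | 4.0 | 3.3 | 4.3 |
| 6, 0.15 | 2.6 | 3.3 | 3.4 |

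As a check, k = 3 and f = 0.5 gives t = 6, and 12 × (720 + 90)/(1728 + 108) = 5.29.

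Using the actual time is closer to 6.0 than using the score as week 36 in every row. It does not recover 6.0. It also relies on a straight-line course, which this example has by construction.

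**5. Chance that the t-test detects the rise.** This was simulated with n = 15, each subject relapsing with probability 0.6, relapsers +10 (SD 4), others 0 (SD 2), and only relapsers leaving. With nobody leaving it is about 0.975.

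| k, f | As week 36 | Excluded |
|---|---|---|
| 3, 0.50 | 0.95 | 0.78 |
| 3, 0.15 | 0.86 | 0.78 |
| 6, 0.50 | 0.93 | 0.31 |
| 6, 0.15 | 0.64 | 0.31 |

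Exclusion detects relapse less often in all four rows.

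**6. When the bias vanishes.** Take 3 leavers with a true rise of 12 and 12 stayers with a rise of 2. The true mean is (36 + 24)/15 = 4.0. Using the exit score gives 2.4, 3.2 or 4.0 when one third, two thirds or all of the rise is present at exit. Excluding the leavers gives 2.0.

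**The case against.** Four objections have force.

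*The plan does not say that the early score becomes the week-36 value.* Section 5.2 is about which visit a leaver attends. A reader might infer that early leavers are counted as being in remission. The documents do not support that: the endpoint is a group mean change and no subject is classified. What stands is that the visit keeps the week-36 name and nothing in Section 7.2.3 keeps its PASI out.

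*Not everyone who leaves is affected.* A reader might take Section 5.2 to reach every exit after week 24. Section 8.7.2 allows no assessment after withdrawal of consent, and death or loss to follow-up yields no visit. The remaining group may be small. Its size depends on how exits are classified, which the documents do not settle.

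*Relapse need not be understated.* A reader might infer that the rule always favours the drug. It does so only if disease is still worsening at exit. If the flare is complete there is no bias, and if PASI is still falling the bias reverses. An early score may also be the only record of the relapse that caused the exit, so removing it can hide more than it corrects (steps 4 to 6).

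*The larger timing problem lies elsewhere.* On the 56 ± 7 day interval every completer is seen at about week 32. Under steady worsening that captures 8/12 = 0.67 of the week-36 change (0.58 to 0.75 across the window), a bigger loss than most rows in step 3. This is correct, and the two matters should be settled together. It does not supply the missing rule for early exits.

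It is also fair that this is a 15-subject open-label pilot, that Section 7.2.3 calls the analysis exploratory, and that nothing changes if nobody leaves after week 24.

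**Conclusion.** The concern holds as a conflict between a stated visit rule and the endpoint definition, left open by the analysis section. For subjects who withdraw after week 24 other than by withdrawing consent, a PASI taken well short of 16 weeks off drug can enter the week-36 mean. Entry as week 36 is the natural reading of the label, but it is not stated.

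The direction is conditional on the course of disease at exit. The size cannot be derived from the documents, which give neither a post-week-24 drop-out rate nor a relapse course. Under steady worsening with exit at week 28 the dilution is 4% to 22% for 1 to 5 leavers of 15. If only relapsers leave, and leave early in relapse, it can be much larger (6.0 falling to 2.6 with 6 of 15 leaving). The primary endpoint is unaffected. The point is worth correcting because it bears on the only durability result and the correction is cheap.

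**What to change.** In Section 5.2, call the visit after a post-week-24 exit an early follow-up visit.

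In Section 7.2.3, state that:
- a PASI from an early follow-up visit is not a week-36 value, but it is not discarded. It is analysed at its actual time since the last dose, for example in a repeated-measures model of PASI on days since last dose, with the assumed shape over time stated;
- the week-24 to week-36 mean change is shown with and without early-visit values;
- the number who left after week 24 because of worsening, or to start other PRP therapy, is reported alongside as a sensitivity count of relapse.

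A week-36 analysis window is needed for these rules to work. The Visit 7 interval in Section 5.1.10 conflicts with week 36 and with the 16 weeks in Section 3.2.3, and the passages must be reconciled when that window is set.

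**Cost.** A few sentences and a little more analysis, with no new visits or procedures. Visit dates (Section 9.2.3), withdrawal reasons (Section 8.7.2), medication changes at Visit 7 (Section 5.1.10) and the home-injection diary (Section 6.2) are already collected. The real price is precision. The analysis without early values has a wider interval and a lower chance of detecting relapse, which can be material if many leave (step 5). That is why both versions should be shown.
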